## ■ Objective

The main goal of this study is to test the efficacy of a peer-facilitated telemedicine HCV treatment implementation strategy for people who use drugs versus local HCV treatment referral for achieving HCV sustained viral response at 12 weeks post-treatment (SVR12).

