### Study Arm 1: Tele-HCV Treatment Arm Procedures:

Participants allocated to telemedicine intervention arm are scheduled for treatment assessment by a study clinician. For a majority of participants, this will also be the treatment initiation visit. If additional studies are necessary for routine treatment decision making, peers will assist participants in navigating health system barriers and arrangement of second telemedicine visit. The telemedicine study clinician will perform a standard of care hepatitis C treatment initiation history and submit a prescription for DAAs. Prior authorizations will be completed by study clinician pharmacist.

All patients initiating treatment will be prescribed HCV medication treatment for 4 weeks at a time. The majority of patients will require two separate dispensations at week 0 and week 4 for a total of 8 weeks of medications, with a small subset requiring third, 4-week dispensation for a total of 12 weeks of therapy. The study clinical pharmacist will check in with the participant by telephone or telemedicine visit at week 0, week 4, and end of treatment to 1) determine general medication tolerance, 2) assess quality of adherence and 3) dispense medications by mail or ensure medications received, depending on participant's insurance. Peers will assist participants in keeping telehealth appointments and navigating medication pick up or storage, if not mailed directly to the home. Participants who report new onset of jaundice or other signs of hepatic decompensation during participation will be scheduled for a follow up telemedicine visit with a physician by the research assistant, receive repeat laboratory studies if needed, and if necessary, be referred to local providers for ongoing medical care. If problems or side effects arise during treatment, participants will call the research assistant, who will connect them to a study clinician.

HCV labs will be repeated at 12 weeks post end of treatment and results will be relayed to the participant in the SVR12 follow up visit with the research assistant, along with follow up surveys. Those successfully achieving SVR12 will be counseled on ongoing harm reduction methods. Those showing persistent HCV viremia at 12 weeks post treatment will be referred to community-based HCV treatment providers for treatment re-initiation. All will be scheduled for 36 week post end of treatment survey visit.

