#### Study Arm 2: Community Linkage-To Care Arm (Control Condition) Procedures:

Participants allocated to the community linkage-to-care arm will complete screening, be offered enrollment, and undergo informed consent as in the telemedicine arm. Following study inclusion and enrollment, research staff will refer the participant to a local community health clinic to engage in hepatitis C care and seek treatment. Peers will assist patients to engage with local primary care and health plan resources and will receive an information sheet on optional clinics to attend and questions to ask their provider. TAU participants will be encouraged to take this to their visit. Research assistants will outreach to participants regularly to determine if they have engaged in local health resources and schedule assessment visits. A bidirectional release of information will be requested. The study clinical pharmacist or research assistant will assess adherence medication adherence at week 4 and end of treatment via telephone. SVR12 laboratory testing will be performed by the community provider with at least one telephone reminder prior to lab due date. 12 weeks post end of treatment study assessments will coincide with SVR12 lab results visit and 36 week post end of treatment assessments performed as in the telemedicine arm.

Chart abstraction for participants in both arms will be performed in order to assess the number of and types of interactions the peers have with participants.

In either arm, participants who do not initiate treatment by 12 weeks after randomization will begin their assessment timeline, mirroring treatment timeline for an 8-week direct acting antiviral regimen. For these participants, the study research assistant will collect study assessments at week 16 (corresponding to 4-week post-treatment initiation), week 20-22 (corresponding to end of treatment visit), week 32 (corresponding to 12 weeks post-treatment visit), and week 56 (corresponding to 36

weeks post-treatment visit) after randomization; the primary study outcome will be assessed at 32 weeks after randomization.

Participant Assessments:

Phase 1:

- Blood draw and DBS specimen collection for HCV RNA and Hepatitis B core antibody

Phase 2:

Assessment/Activity	Pre-Screen	Screen	Baseline (Week 0)	4-Week after treatment initiation	End of Treatment	12-week Post-Treatment	***36-Week Post Treatment Completion	As Needed

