#### **Study Measures:**

The primary outcome is sustained viral response at 12 weeks post treatment (SVR12). Secondary outcomes include a) HCV treatment initiation, b) HCV Treatment completion (filled final prescription and self-reported > 90% HCV treatment pills taken), c) engagement with harm reduction resources, d) substance use, e) perceived stigma, and f) engagement in addiction treatment resources. Exploratory endpoints include a) treatment satisfaction with hepatitis C treatment, adapted from the single-item Medication Satisfaction Questionnaire, and b) reinfection vs. virologic relapse/failure.

Adherence to Phone Visits: Adherence to these phone visits is defined as +/- 5 days

Prescreen, baseline and follow-up surveys collected in the field or via phone will first be documented on paper forms. These will then be entered into REDCap by the RA. The source documents will be kept in a locked file cabinet in a secure location.

Qualitative interviews will be recorded on an encrypted recorder and stored on a secure, encrypted computer.

Survey data will be used to determine HCV status of participants with a detectable plasma HCV RNA, which were collected on or after SVR12 timepoint (either 12 weeks after end of treatment for those who initiated treatment or 32 weeks after randomization for those who did not initiate treatment). The primary SVR12 outcome will be sustained viral response 12 weeks after treatment for participants who initiated treatment within 6 months. Participants who did not start treatment within 6 months will be considered treatment failure. Measuring detectable plasma HCV RNA for both participants who initiated and did not initiate within 6 months of randomization will provide a framework to assess for potential biasing impact of spontaneous clearance on assumption of treatment failure for participants who did not initiate treatment within 6 months.

**Probable Relapse/Failure:** Probable virologic relapse or failure is defined as a detectable plasma HCV RNA 12 weeks or more after the end of treatment if a) participant denies any injection drug use, or b) participant injecting drugs but notes 100% adherence to recommendations on Safe injection practices, including use of clean works (cooker, cotton, rinse) with every injection.

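### The week-32 primary assessment has no exception for participants who start treatment after week 12 but within 6 months, whose outcome is defined elsewhere as SVR 12 weeks after treatment

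*Combined protocol and SAP*

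**What the plan says.** Two sections set the time of the primary outcome.

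- **Study Arm 2: Community Linkage-To Care Arm (Control Condition) Procedures.** A paragraph that applies to both arms says that "participants who do not initiate treatment by 12 weeks after randomization will begin their assessment timeline". It describes this calendar as "mirroring treatment timeline for an 8-week direct acting antiviral regimen". It lists visits at weeks 16, 20-22, 32 and 56 after randomization and ends: "the primary study outcome will be assessed at 32 weeks after randomization". It does not mention a participant who starts treatment after week 12.
- **Study Measures.** "The primary SVR12 outcome will be sustained viral response 12 weeks after treatment for participants who initiated treatment within 6 months". The next sentence reads "Participants who did not start treatment within 6 months will be considered treatment failure", and the paragraph counts the 6 months from randomization. Just before this, in a sentence on classifying participants with detectable RNA, the SVR12 timepoint is given as "either 12 weeks after end of treatment for those who initiated treatment or 32 weeks after randomization for those who did not initiate treatment".

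The Study Arm 1 procedures tie the draw to treatment ("HCV labs will be repeated at 12 weeks post end of treatment") and foresee 8-week courses for most participants and 12-week courses for a small subset. Under Data Analysis, Hypothesis 1, a missing viral load counts as non-suppressed.

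**The concern.** The two sections define their groups differently. The fixed calendar applies to anyone with no start by week 12. The endpoint definition applies to anyone with a start within 6 months. A participant who starts between those two dates belongs to both groups and has two different times for the primary outcome.

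If the fixed calendar is followed as written, an RNA taken on treatment or early after treatment could be recorded as SVR12. If that RNA is instead rejected as too early and no later sample is drawn, a participant who may be cured is scored as non-suppressed under the missing-data rule. The two errors act in opposite directions. The plan states a tolerance only for phone visits (5 days either way), gives none for the SVR12 draw, and does not say how an RNA taken before 12 weeks post-treatment is to be handled. If late starts are more common in one arm, the error would not cancel between arms.

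**Working it through.** **Inputs**

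- Trigger for the fixed calendar: no start by week 12 (Study Arm 2 procedures).
- Regimen that the calendar mirrors: 8 weeks (same place).
- Course lengths foreseen: 8 or 12 weeks (Study Arm 1 procedures, so stated for the telemedicine arm).
- Limit for a start that can count as success: 6 months from randomization (Study Measures). Assumption: 6 months = 26 weeks (365.25 / 2 / 7 = 26.1).

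**Step 1: reproduce the plan's calendar.** 12 + 4 = week 16; 12 + 8 = week 20; 12 + 8 + 12 = week 32; 12 + 8 + 36 = week 56. All agree with the plan. Week 32 is therefore the SVR12 time for an 8-week course started exactly at week 12.

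**Step 2: find the overlap.** Both rules apply to a start week *t* with 12 < *t* ≤ 26, a span of 26 − 12 = 14 weeks.

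**Step 3: time off treatment at week 32.**

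- 8-week course: 32 − (*t* + 8) = 24 − *t*
- 12-week course: 32 − (*t* + 12) = 20 − *t*

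**Step 4: when SVR12 is actually due.**

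- 8-week course: *t* + 8 + 12 = *t* + 20
- 12-week course: *t* + 12 + 12 = *t* + 24

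| Start week | Weeks off treatment at week 32 (8-week / 12-week course) | SVR12 due at week (8-week / 12-week course) |
|---|---|---|
| 13 | 11 / 7 | 33 / 37 |
| 16 | 8 / 4 | 36 / 40 |
| 20 | 4 / 0 | 40 / 44 |
| 24 | 0 / −4 | 44 / 48 |
| 26 | −2 / −6 | 46 / 50 |

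A negative value means that treatment is still running at week 32.

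**Step 5: read off the result.** For *t* > 12, 24 − *t* is below 12 and 20 − *t* is below 8, so week 32 is too early for every start in the overlap. Treatment is still running at week 32 for starts after week 24 with an 8-week course (last 2 of the 14 weeks) and for starts after week 20 with a 12-week course (last 6 of the 14 weeks).

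The documents do not give the number of late starters in either arm, so no effect on the estimated difference can be computed.

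**The case against.** The strongest reply is that Study Measures is where the endpoint is defined, and it already gives a direct rule for this group: SVR 12 weeks after treatment for any start within 6 months. Its parenthesis ties week 32 to participants who did not initiate. The paragraph in the Study Arm 2 procedures is about scheduling, and its visits stand in for treatment-based visits, which are needed only when there is no treatment date. The Objective, the treatment-based draws in both arms' procedures and the schedule of assessments all point the same way. On that reading, harm arises only if staff or analysts depart from the endpoint definition.

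As an account of intent this is probably right. It does not repair the text. The scheduling paragraph expressly names the primary outcome, its group is those not started by week 12 rather than those never treated, and no section says which rule prevails. Staff booking visits would reasonably work from that paragraph.

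Three parts of the reply stand. The timing error arises only if the paragraph is followed literally. A majority of telemedicine participants are expected to start at their first visit, so late starts in that arm may be few, although this says nothing about the control arm. And the arms' different routes for the SVR12 draw (community partner laboratories versus the community provider) affect all starters, so they are a separate matter.

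**Conclusion.** The concern holds. For starts after week 12 and up to about week 26, the plan gives two incompatible times for the primary outcome. Applied literally, the week-32 rule yields an assessment that is never a true SVR12: 0 to under 12 weeks after an 8-week course, or 0 to under 8 weeks after a 12-week course, or else on treatment. This rests on the stated course lengths and on taking 6 months as 26 weeks. Neither the size nor the direction of any bias is known, and no shift in the result is claimed. The conflict should be fixed because it concerns the primary endpoint of a non-blinded trial, and it should be settled before outcomes are read.

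**What to change.** Amend the paragraph in the Study Arm 2 procedures to agree with Study Measures.

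1. Limit the week-32 primary assessment to participants with no start within 6 months. They are failures by rule, and their week-32 RNA serves the check on spontaneous clearance. Flag anyone who starts between 6 months and week 32: they could be up to 32 − 26 = 6 weeks into treatment at that draw, and a suppressed result should not be read as spontaneous clearance.
2. State that anyone who starts within 6 months moves to the treatment-based calendar, with the primary RNA 12 weeks after actual end of treatment. The latest draw is then about week 46 (8-week course) or week 50 (12-week course).
3. Say whether the 36-week post-treatment visit of late starters moves or stays at week 56, and whether the week-16 and week 20-22 visits are repeated for those who have already had them.

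The cost is one clause and a re-timed draw for late starters; treatment does not change. The latest draw still falls 56 − 46 = 10 or 56 − 50 = 6 weeks before the existing week-56 visit. The primary result of the latest starters arrives 46 − 32 = 14 or 50 − 32 = 18 weeks after week 32. If their 36-week post-treatment visit is moved, it falls as late as 26 + 8 + 36 = week 70 or 26 + 12 + 36 = week 74.

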#### **Study Measures:**

The primary outcome is sustained viral response at 12 weeks post treatment (SVR12). Secondary outcomes include a) HCV treatment initiation, b) HCV Treatment completion (filled final prescription and self-reported > 90% HCV treatment pills taken), c) engagement with harm reduction resources, d) substance use, e) perceived stigma, and f) engagement in addiction treatment resources. Exploratory endpoints include a) treatment satisfaction with hepatitis C treatment, adapted from the single-item Medication Satisfaction Questionnaire, and b) reinfection vs. virologic relapse/failure.

Adherence to Phone Visits: Adherence to these phone visits is defined as +/- 5 days

Prescreen, baseline and follow-up surveys collected in the field or via phone will first be documented on paper forms. These will then be entered into REDCap by the RA. The source documents will be kept in a locked file cabinet in a secure location.

Qualitative interviews will be recorded on an encrypted recorder and stored on a secure, encrypted computer.

Survey data will be used to determine HCV status of participants with a detectable plasma HCV RNA, which were collected on or after SVR12 timepoint (either 12 weeks after end of treatment for those who initiated treatment or 32 weeks after randomization for those who did not initiate treatment). The primary SVR12 outcome will be sustained viral response 12 weeks after treatment for participants who initiated treatment within 6 months. Participants who did not start treatment within 6 months will be considered treatment failure. Measuring detectable plasma HCV RNA for both participants who initiated and did not initiate within 6 months of randomization will provide a framework to assess for potential biasing impact of spontaneous clearance on assumption of treatment failure for participants who did not initiate treatment within 6 months.

**Probable Relapse/Failure:** Probable virologic relapse or failure is defined as a detectable plasma HCV RNA 12 weeks or more after the end of treatment if a) participant denies any injection drug use, or b) participant injecting drugs but notes 100% adherence to recommendations on Safe injection practices, including use of clean works (cooker, cotton, rinse) with every injection.

**Probable Reinfection:** Probable reinfection is defined as a detectable plasma HCV RNA 12 weeks or more after the end of treatment if a) participant completes full course of DAA regimen, and b) participant notes injection behavior of substantial risk, including i) Receptive use of injection equipment (needles, cotton, cooker) from someone of either unknown HCV serostatus or known positive serostatus on one or more occasion and ii) use happened between end of treatment and HCV RNA test

**Indeterminant Relapse vs Reinfection:** Indeterminant virologic relapse vs reinfection is defined as a participant with a detectable plasma HCV RNA 12 weeks or more after the end of treatment in participants a) not completing DAA regimen, and b) with injection behavior of substantial risk, as noted above.

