Pre-Screening Survey	X							
Demographics		X						
Inclusion/Exclusion		X						
Rapid HCV Test	X							
CPT Assessment		X						
Participant Survey								
Medical Care History			X		X	X	***X	
Barriers to treatment			X		X	x	***X	
Engagement with Harm Reduction & Substance Use Treatment			X	X	X	X	***X	
Substance Use			X	X	X	X	***X	
Perceived Stigma of Drug Use			X	X	X	X	***X	
HCV Treatment History			X		X			
HCV Treatment Completion					X			
HCV Treatment Adherence				X	X			
Treatment Satisfaction					X			
Experience with Telemedicine					**X			
Experience with Peer Support Specialist					**X			
Blood Draw/ Medical Procedures								
HCV RNA		X				X		
Hepatitis B Sag		X						
Hepatitis B SAg		X						
Hepatitis B cAb		X						
Hepatitis A Ab		X						
CMP		X				X		

CBC		X				X	
INR/prothrombin		X					
HCV genotype		X					
B-HCG (women<50)		X					
SC Reviews Labs		X				X	
Ultrasound							**X
Telemedicine Visit			**X				
Medication Counseling			**X	**X	X*		
HCV Genotype and Resistance Testing							**X
Chart Abstraction					X	X	
Peer interaction log					X		
HCV treatment provider visits					X		
Administrative							
Written informed consent		X					
Locator Form	X		X	X	X	X	X
Master Enrollment Log			X				
Progress Note Check List	X	X	X	X	X	X	X
Reportable Events Log							X
Adverse Event							X
Inventory Form							X
Visit Compensation Log	X		X	X	X	X	X

\*\*\*X: 36 Week Survey only if participant qualifies

\*\*X: Only Telemedicine Pt.

\*X: Number of weeks of treatment depends on ppt.

Participants complete brief REDCap surveys regarding symptoms, substance use, and harm reduction engagement at baseline, 4 weeks, end of treatment, 12 post end of treatment, and 36 weeks post end of treatment. These surveys will be conducted over the phone or in person.

Participants undergo phlebotomy at screening and 12 post end of treatment.

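### For participants not started by week 12, the last dedicated HCV-treatment item comes 4 to 6 weeks before the 6-month start window closes, and no source is named to date a later start

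*Combined protocol and SAP*

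**What the plan says.** Study Measures defines the endpoint by time of start: "The primary SVR12 outcome will be sustained viral response 12 weeks after treatment for participants who initiated treatment within 6 months". Its complement is "Participants who did not start treatment within 6 months will be considered treatment failure". The same section plans to use HCV RNA in starters and non-starters to check whether spontaneous clearance biases that failure rule.

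The Study Arm 2 section, in a paragraph that applies to either arm, says that "participants who do not initiate treatment by 12 weeks after randomization will begin their assessment timeline, mirroring treatment timeline for an 8-week direct acting antiviral" course. After a first visit at week 16, the later visits are "week 20-22 (corresponding to end of treatment visit), week 32 (corresponding to 12 weeks post-treatment visit), and week 56". It adds that "the primary study outcome will be assessed at 32 weeks after randomization".

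The Phase 2 schedule under Participant Assessments marks the relevant rows as follows:

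- *HCV Treatment History*: Baseline and End of Treatment.
- *HCV Treatment Adherence*: 4-Week and End of Treatment.
- *HCV Treatment Completion*: End of Treatment.
- The abstraction row "HCV treatment provider visits": End of Treatment.
- The *Chart Abstraction* heading: End of Treatment and 12-week Post-Treatment.
- *Medical Care History* and *Barriers to treatment*: Baseline, End of Treatment, 12-week and 36-week visits, the last only for participants who qualify.

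In telemedicine the study clinician prescribes, and the study pharmacist makes contact at week 0, week 4 and end of treatment (Study Arm 1). Control participants are treated by local clinics. Research assistants contact them regularly about engagement with local care, and a release of information is requested (Study Arm 2).

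**The concern.** A rule that counts starts up to 6 months needs a record of starts up to 6 months. For participants on the fixed clock, the dedicated questions are asked for the last time before that date. No section names the record that sets the start date.

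The exposure differs by arm. A telemedicine start creates a study record when the prescription is written. A control start takes place in an outside clinic and must be found. In a non-blinded superiority comparison, a control start that is not found counts as failure, which favours telemedicine.

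The planned check on spontaneous clearance is exposed too. If a start is unrecorded and the week-32 RNA is undetectable, suppression by treatment would be read as clearance without treatment.

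**Working it through.** **Inputs.** Fixed clock starting at week 12, 8-week regimen, visits at weeks 16, 20-22, 32 and 56 (Study Arm 2). Start window of 6 months from randomization, and a visit window of plus or minus 5 days, stated for phone visits (Study Measures). Courses of 8 or 12 weeks (Study Arm 1).

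**1. The plan's own timeline reproduces.** 12 + 4 = 16; 12 + 8 = 20; 20 + 12 = 32; 20 + 36 = 56.

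**2. Six months in weeks.** 180/7 = 25.7 and 183/7 = 26.1, so about 26.

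**3. Window left after the last dedicated item.**

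| Visit at week | Weeks left to 26 | Share of the 26 weeks | Share of weeks 12-26 |
|---|---|---|---|
| 20 | 6 | 6/26 = 23% | 6/14 = 43% |
| 22 | 4 | 4/26 = 15% | 4/14 = 29% |
| 22 plus 5 days (22.7) | 3.3 | 13% | 23% |

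These are shares of the calendar, not of starts.

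**4. Where week 32 falls for a start in weeks 22-26.**

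- 8-week course: treatment ends at 22 + 8 = 30 to 26 + 8 = 34. SVR12 falls at 30 + 12 = 42 to 34 + 12 = 46.
- 12-week course: treatment ends at weeks 34 to 38, and SVR12 falls at weeks 46 to 50.

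The week-32 RNA is therefore at most 2 weeks after the end of treatment (32 - 30) and as much as 6 weeks before it (38 - 32). It is never an SVR12 result for these participants.

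**5. The timing conflict is wider than the gap.** An 8-week course begun at week s reaches SVR12 at s + 20. This is later than week 32 for any start after week 12; a start at week 14, for example, gives week 34. A course begun after week 14 is also unfinished at week 22 (14 + 8 = 22), when completion is asked for the last time on the fixed clock.

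**6. Effect on the result.** The control SVR12 rate is understated by (share of controls whose qualifying start is missed) x (share of those who would have been SVR12 successes). The documents give neither factor, so no figure in percentage points follows.

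**The case against.** The strongest reply is that other routes exist. The *Chart Abstraction* heading is marked at 12 weeks post-treatment, which is week 32 for non-starters and after the window closes. *Medical Care History* is asked at weeks 32 and 56, and the survey instruments are not in the document, so it may cover HCV treatment. Control outreach has no stated end, and a release of information is requested. Study Measures scores failure on whether treatment started, not on a survey answer, and Data Analysis ties initiation to a filled first prescription. Late starters may also be moved to their own treatment-based visits, which would give them a true End of Treatment visit.

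Much of this stands. A reader might infer from the schedule that starts after week 22 are not captured at any visit. The document does not support that, because the routes above could find them. Nor does it show that such a participant is certain to be scored a failure.

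What the reply does not supply is a specified source. The stated purpose of chart abstraction is to describe peer interactions, and the provider-visit row lacks the 12-week mark. Outreach asks about engagement with local resources and is not tied to week 26. Nothing says that late starters are re-anchored to their own dates; the fixed clock, read literally, keeps them at week 32.

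The reply is also right that a start date alone cannot score these participants, because their SVR12 date falls after week 32. The repair has to cover both.

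**Conclusion.** The point holds in a limited form. For participants not started by week 12, dedicated HCV-treatment ascertainment ends 4 to 6 weeks before the start window closes (3.3 weeks if a week-22 visit slips by 5 days), and no later item is specified to record a dated start. The likely direction of error favours telemedicine.

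The size is unknown. It would be tempting to turn the 15% to 23% of the window into a bias of several percentage points. That would need an assumed rate of late control starts, an assumed cure rate, and the premise that every such start is missed.

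The reach is also limited. The initiation test at 4 weeks and the completion test at 12 weeks are not affected by starts in weeks 22-26. After viremia at the SVR12 visit, Study Arm 1 states "Those showing persistent HCV viremia at 12 weeks post treatment will be referred to community-based HCV treatment providers for treatment re-initiation". A reader might infer that unrecorded re-treatment affects the primary outcome. It does not; it bears only on later RNA results in the exploratory relapse and reinfection endpoint.

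The conclusion assumes that 6 months is about 26 weeks and that the table columns were read correctly. The lower part of the schedule, as extracted, has one trailing column fewer. The abstraction marks used here line up with the End of Treatment and 12-week columns, and nothing is concluded about abstraction at 36 weeks.

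**What to change.** 1. In the Phase 2 schedule, mark *HCV Treatment History* and the provider-visit abstraction row at the 12-week post-treatment / week-32 visit in both arms. Record first-fill and stop dates, and state that the 6-month start status is set from them.
2. For late starters, ask *HCV Treatment Completion* after the actual end of treatment.
3. Repeat *HCV Treatment History* at the 36-week / week-56 visit, so that later RNA results can be interpreted for the exploratory endpoint.
4. Exclude any RNA drawn after a first DAA dose from the spontaneous-clearance check.
5. Reconcile Study Arm 2 (primary outcome at week 32) with Study Measures (12 weeks after end of treatment) for participants who start between week 12 and 6 months. Their SVR12 should be scored on an RNA at or after their own 12-week post-treatment date.

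Items 1 to 3 use existing questions and one existing abstraction row. They cost a few extra minutes per visit and a REDCap form change; item 2 may move the timing of one question for late starters. Item 4 is a line in the analysis plan. Item 5 needs a decision on timing and, for late starters, an RNA result later than week 32.

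### The relapse-versus-reinfection rules for exploratory endpoint b never use genotype, so a viraemic participant with a changed genotype can be labelled probable relapse on reported behaviour

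*Combined protocol and SAP*

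**What the plan says.** Study Measures lists "b) reinfection vs. virologic relapse/failure" as an exploratory endpoint and names the source of the classification: "Survey data will be used to determine HCV status of participants with a detectable plasma HCV RNA". Three classes follow, each starting from a detectable plasma HCV RNA at least 12 weeks after the end of treatment.

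- **Probable relapse/failure:** "participant denies any injection drug use, or b) participant injecting drugs but notes 100% adherence to recommendations on Safe injection practices".
- **Probable reinfection:** "participant completes full course of DAA regimen, and b) participant notes injection behavior of substantial risk", where the risk is receptive sharing of equipment between the end of treatment and the RNA test.
- **Indeterminate:** "not completing DAA regimen, and b) with injection behavior of substantial risk, as noted above".

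The Phase 2 schedule under Participant Assessments marks HCV genotype once, at Screen, with no arm restriction. It has one other genotype row, "HCV Genotype and Resistance Testing", with a single mark in the last column; the footnote to that mark reads "Only Telemedicine Pt". The compensation table under Recruitment Methods pays for reinfection labs at 36 weeks after treatment, but their content is defined nowhere and the schedule has no matching laboratory entry. The Study Arm 2 procedures leave SVR12 testing of controls to the community provider, do not mention genotype, and provide for a bidirectional release of information. The Data Analysis section does not mention genotype or this endpoint.

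**The concern.** The endpoint asks whether viraemia after treatment is the old virus or a new one. A genotype that differs from screening bears directly on that question, and the plan already provides for the baseline half of the comparison. The rules instead let reported injecting decide between relapse and reinfection.

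Participants who under-report injecting or sharing move from reinfection to relapse, and no laboratory result can move them back. The split would then show too many treatment failures and too few new infections after cure.

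The survey answers are collected by research staff or peer care coordinators, and Hypothesis 4 expects less substance use and more harm-reduction engagement in the telemedicine arm. If reported risk behaviour differs between arms, whether through real change or through reporting, the labels shift with it. A step that does not depend on self-report would limit this.

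**Working it through.** The plan states no figure for this endpoint, so there is none to reproduce. The check has two parts.

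**1. Do the rules respond to a genotype change?** The inputs are the three definitions under Study Measures. A viraemic participant is described by injecting (yes/no), 100% safe practice (yes/no), receptive sharing (yes/no) and completion of the DAA course (yes/no). Dropping contradictory combinations (a non-injector with injecting practices; fully safe practice together with receptive sharing) leaves 8 profiles.

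| Reported behaviour | DAA course completed | DAA course not completed |
|---|---|---|
| No injecting | relapse | relapse |
| Injecting, 100% safe | relapse | relapse |
| Injecting, receptive sharing | reinfection | indeterminate |
| Injecting, not 100% safe, no receptive sharing | no label | no label |

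Adding a genotype change to each profile alters the label in 0 of 8, because no rule has a genotype term. Four of the 8 stay at probable relapse despite the change. With a genotype-first step, all 8 would become probable reinfection when the genotype has changed. That alters 8 − 1 = 7 labels: 4 from relapse, 1 from indeterminate and 2 from no label.

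**2. How much could genotype recover?** Both inputs here are assumptions; the documents give neither.

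Let g be the share of reinfections with a changed genotype. Under random mixing with genotype shares p, g = 1 − Σp².

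- 95/5%: 1 − (0.9025 + 0.0025) = 0.095
- 90/10%: 1 − (0.81 + 0.01) = 0.18
- 80/15/5%: 1 − (0.64 + 0.0225 + 0.0025) = 0.335
- 70/20/10%: 1 − (0.49 + 0.04 + 0.01) = 0.46
- 60/15/15/10%: 1 − (0.36 + 0.0225 + 0.0225 + 0.01) = 0.585

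Let u be the share of true reinfections in which the participant denies injecting or claims fully safe practice. The current rules label a share u of true reinfections as relapse. With genotype available for all and taking precedence, the share is u(1 − g).

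| u | Current rules | g = 0.095 | g = 0.585 |
|---|---|---|---|
| 10% | 10% | 9.05% | 4.15% |
| 25% | 25% | 22.6% | 10.4% |
| 50% | 50% | 45.25% | 20.75% |

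Where the later genotype is missing, the share stays at u.

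**The case against.** The strongest reply is that this is an exploratory endpoint with no hypothesis or model attached, that its classes are called probable, and that an indeterminate class already admits uncertainty. All of that is true, and it limits the weight of the point. It does not repair the rule: the indeterminate class is reserved for non-completers who report risk, so it does not catch a participant who denies injecting and has a changed genotype.

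Three stronger readings are tempting, and the documents do not support them.

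- **That the endpoint is derived differently in the two arms.** As written, the rules use RNA, reported behaviour and DAA completion, and are identical in both arms. The later genotype row is telemedicine only, but it appears to be as needed and is not stated to be post-treatment. It could equally belong to the pre-treatment work-up, since the Study Arm 1 procedures foresee additional studies for treatment decisions. The table is broken at this point (seven columns against eight in the header), so reading its mark as As Needed rests on position; the adverse event and reportable event rows share that column. The 36-week reinfection labs carry no arm restriction and might include genotype. An asymmetry would arise only if genotype were brought into the rule without being sought equally in both arms.
- **That the rules rest on self-report alone.** Entry to every class needs a laboratory RNA result, and DAA completion, if read as in the secondary outcome, includes a filled final prescription. It is the step between relapse and reinfection that turns on reported behaviour.
- **That the trial's efficacy result suffers.** SVR12 depends on viral load, with missing values counted as non-suppressed; these labels do not enter it.

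The magnitude is also open to challenge. The assumed mixes do not bound the answer, and snowball recruitment through personal networks makes random mixing doubtful. That objection stands, so the figures serve only as illustration.

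**Conclusion.** The point holds for exploratory endpoint b and no further. Followed as written, the rules label a viraemic participant with a changed genotype as probable relapse/failure whenever that participant denies injecting or reports fully safe practice. This follows from the definitions and needs no assumption.

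The size does rest on assumptions. For the mixes tried, about 0.1 to 0.6 of reinfections would show a genotype change, and fewer if recruited networks share genotypes. If a quarter of true reinfections were reported as no or safe injecting, mislabelling would fall from 25% to between 22.6% and 10.4%, given complete genotyping. The number of viraemic participants is not given either, so no count can be stated. Genotype would not settle every case, because reinfection with the same genotype remains unresolved.

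SVR12 and the secondary outcomes are untouched. The change is still worth making, because it is cheap and can be settled before labels are assigned.

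**What to change.** 1. **Rule.** Under Study Measures, put a first step before the three definitions: if the genotype or subtype at post-treatment viraemia differs from the participant's screening result, classify as probable reinfection whatever the self-report. If it is the same or unavailable, apply the existing behavioural rules.
2. **Source.** State that the later genotype is sought in the same way for viraemic participants in both arms, from the 12-week or 36-week labs or from the community record under the release of information. Amend the schedule footnote to match, and define the content of the 36-week reinfection labs.
3. **Reporting.** By arm, give the numbers classified by genotype, by self-report, and with genotype missing. Show the self-report-only classification as a sensitivity analysis.

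The cost is a short addition to the definition, a footnote, and a few assays or record requests. The documents describe no retained control specimen suitable for genotyping, so some control genotypes will probably be missing. Adopting the rule without the second item would create the arm difference that the present rules avoid, so the two should be changed together.
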